9 STATISTICAL CONSIDERATIONS

9.1 General Design Issues

Aim 1 Demonstrate the feasibility of identifying a diverse cohort of eligible patient/care partner dyads and implementing the PPC program by trained facilitators (e.g. social worker, nurse, nursing assistant). A total of 160 patients or patient-care partner dyads (~50% White, 45% Black, and of those 6% Hispanic/Latino) will be identified as eligible from the geriatrics or primary care practices of three health care systems. Eligible PLWDM and their care partners will be identified through the EHR. Implementation endpoints demonstrating feasibility will include:

1. Identification of care partners for 50% of eligible PLWDM identified in Aim 1,
2. Documentation of PPC discussion in 35% of eligible participants in the EHR, which will be ascertained using review of electronic medical records and an established Natural Language Processing model,
3. Evaluation of implementation endpoints (acceptability, appropriateness, feasibility, fidelity, and potential for future adoption of the intervention) assessed through chart review and semi-structured participant interviews with some patients, patient-care partner dyads, facilitators, and clinicians.

Aim 2 Demonstrate feasibility of pragmatically assessing the following clinical outcomes using the EHR among enrolled patients and patient-care partner dyads measured up to 2 months (60 days) after documented PPC discussion:

1. days at home (primary clinical outcome),
2. total medications, and
3. new referrals to specialist physicians.

We have defined the “days at home” variable to include data two months (60 days) prior (pre-visit days at home) to the PPC visit, as well as two months (60 days) after the visit (post-visit days at home). Days at home are days that are spent at home instead of in a hospital or long-term care facility.

Aim 3 Examine key feasibility measures across racial, ethnic, and socioeconomic subgroups including:

1. quantitative measures of enrollment of eligible dyads, documented PPC discussions, and clinical outcomes measures, and
2. Qualitative measures ascertained from chart review and participant interviews, including acceptability and appropriateness.
3. Deploy established algorithms for detecting social factors that may influence patient care priorities, such as housing instability, financial insecurity, or transportation concerns. These algorithms have been previously created and

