We will use findings from Aim 3 to examine key feasibility measures across racial, ethnic, and socioeconomic subgroups to determine further adjustments that may be needed to tailor the intervention to a diverse population. We recognize that a “one size fits all” approach is inappropriate for many historically and structurally marginalized groups and that adjustments may need to be made to the flexibility of the overall intervention protocol. This may include identification of additional implementation or clinical endpoints for examination. Progression criteria for this aim is that we are able to determine the key feasibility measures for a minimum of the +/- 10% proportion of racial, ethnic, and socioeconomic subgroups that mirrors the populations seen in each health system. We will also conduct between-group comparisons on our measure of PPC documentation between Black v. White and those with financial insecurity vs. none (small sample sizes will preclude analysis of Hispanic patients and those with housing instability). If there are significant differences, we will make further adjustments prior to embarking upon a Stage IV ePCT of this intervention.

Table 1. Implementation outcomes and data sources		
	Implementation outcomes	Source of data
Feasibility	Identification of sample Enrollment goals Feasibility of outcome ascertainment	Administrative data Qualitative interviews with clinicians, patients, and care partners NLP

Adoption	Utilization /intent to use	EHR Qualitative interviews with clinicians
Acceptability / appropriateness	Satisfaction with the intervention (content, delivery, credibility) Perceived usefulness and practicality	Qualitative interviews with clinicians, patients, and care partners
Fidelity	Adherence to implementation protocol Quality of implementation	Training records – completion /results- competency Checklist of adherence to protocol -EHR Qualitative interviews- barriers /facilitators to refine implementation strategy

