**Patient Priorities Care Among Persons Living With Mild Cognitive Impairment and
Dementia (IN-TX-PPC)**

NCT06001775

22 January 2026

Quantitative analysis plan

Demographic characteristics will be compared between the groups of patients with and without a Patient Priorities Care (PPC) conversation documented. Categorical variables, including ethnicity, race, and sex, will be summarized using counts and percentages and compared between groups using Fisher's exact test when appropriate. Age will be analyzed as a continuous variable, summarized using means and standard deviations and compared using the Wilcoxon rank-sum test. The p-values of those tests will be reported. All tests will be two-sided.

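### The SAP does not match protocol 9.4.2 on the Aim 3 subgroup comparisons: it omits financial insecurity, does not isolate Black v. White, tests ethnicity, and plans no rate difference or confidence interval

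*Protocol*

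**What the plan says.** Protocol 9.4.2, on Aim 3: "We will also conduct between-group comparisons on our measure of PPC documentation between Black v. White and those with financial insecurity vs. none". It adds in parentheses that "small sample sizes will preclude analysis of Hispanic patients and those with housing instability". The consequence is stated next: "If there are significant differences, we will make further adjustments prior to embarking upon a Stage IV ePCT of this intervention".

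The same paragraph uses Aim 3 findings more broadly "to determine further adjustments that may be needed to tailor the intervention to a diverse population". Its formal criterion concerns representation: "Progression criteria for this aim is that we are able to determine the key feasibility measures for a minimum of the +/- 10% proportion" of subgroups seen in each health system.

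The précis and section 2.2 look for evidence that racial, ethnic and socioeconomic groups are engaged equally before a full trial; section 3 repeats the sentence without the word for equality. Section 9.1 gives the planned mix of the 160 as about "50% White, 45% Black, and of those 6% Hispanic/Latino) will be identified as eligible", and describes how financial insecurity will be found in clinical notes.

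The SAP is one paragraph. It compares demographic characteristics between patients with and without a documented PPC conversation: "Categorical variables, including ethnicity, race, and sex, will be summarized using counts and percentages and compared between groups using" Fisher's exact test where appropriate. Age is compared by the Wilcoxon rank-sum test. It ends: "The p-values of those tests will be reported. All tests will be two-sided".

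**The concern.** Someone who follows the SAP as written would leave out one comparison that the protocol promises and run one that the protocol says the numbers cannot support. For the remaining promised comparison, they could report a p-value for race as a whole that is not the Black v. White p-value.

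The output also falls short of its purpose. The comparison is one input to whether the intervention is adapted before the Stage IV trial, and the protocol looks for evidence of equal engagement. A p-value at this sample size says little about that. The size of the gap, and the range of gaps the data allow, are what a reader needs, and neither is planned as an output.

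**Working it through.** **Side by side**

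| Comparison of PPC documentation | Protocol 9.4.2 | SAP |
|---|---|---|
| Black v. White | Promised | Race tested; contrast not specified |
| Financial insecurity v. none | Promised | Not named |
| Hispanic ethnicity | Ruled out (small numbers) | Tested |
| Rate difference, confidence interval | Not mentioned | Not mentioned |
| Significance level | Not stated | Not stated |

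The SAP groups patients by documentation status, not by race. For a 2x2 table this is the same Fisher test, so that alone is no discrepancy.

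**The plan's own figure.** Section 9.2 sizes the study at 160 for a one-sample test of 40% v. 50% with 80% power. With one-sided 5% (assumed), n = [(1.645·√(0.40·0.60) + 0.842·√(0.50·0.50)) / 0.10]² = 150.5, or 160.3 with continuity correction. The 160 reproduces. It sizes a one-sample test only, so it gives no assurance for a comparison between subgroups.

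**Inputs for the subgroup comparisons.** Group sizes come from section 9.1: 50% of 160 = 80 White, 45% = 72 Black, leaving 8 others. The 35% documentation rate is the green-zone value in 9.4.2, used here as the overall rate. Alpha is assumed to be 0.05, two-sided. All 160 are treated as analysed.

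**Black v. White, 80 v. 72.** Exact Fisher power by full enumeration, White rate higher:

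- 40% v. 30% (10 points): 23%
- 42.5% v. 27.5% (15 points): 47%
- 45% v. 25% (20 points): 72%

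With overall documentation anywhere from 25% to 65%, in either direction, the ranges are 20–27%, 41–54% and 65–80%. The 95% interval half-width is 1.96·√(0.35·0.65·(1/80 + 1/72)) = 0.152, about 15 points.

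For illustration, 33/80 (41%) v. 20/72 (28%) gives p = 0.09. The difference is 13.5 points with a Wald 95% interval of −1.5 to 28 points. The result is non-significant, but it is compatible with a large gap.

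**Race tested as one variable.** Take 34/80 v. 19/72. Black v. White alone gives p = 0.042. Adding the 8 others and using the three-category exact test:

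| Others documented, of 8 | p for race overall |
|---|---|
| 0 | 0.010 |
| 1 | 0.054 |
| 2 | 0.110 |
| 3 | 0.121 |
| 4 | 0.077 |
| 5 | 0.029 |
| 6 | 0.008 |

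With 7 or 8 documented, p is smaller still. The conclusion changes with 1 to 4 of 8 and does not change otherwise.

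**Financial insecurity.** The documents give no split. If 10% to 50% of 160 are insecure (assumed), power for a 10-point gap is 7–24% when the insecure group has the lower rate and 10–25% when it has the higher. The half-width runs from 25 points down to 15.

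**Ethnicity.** Six percent of 160 is 9.6 patients, or 4.3 if the 6% applies only to the 72 Black patients. With 9 or 10 Hispanic patients, power for a 10-point gap is 5–8% and the half-width is 31 to 32 points. This supports the protocol's own decision not to analyse them.

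**The case against.** The strongest reply is that this is a gap between two texts and that nothing has been abandoned. Section 9.4.2 still promises the financial-insecurity comparison, section 9.5 refers back to 9.4, section 9.1 foresees using the social-factor annotations in analyses, and the SAP does not claim to replace any of this. That stands: a reader might infer that the comparison has been dropped, and the documents do not show it. What is missing is a planned analysis for it.

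A reader might also infer that the SAP reports nothing but p-values. It also plans counts and percentages, and from the counts by race and documentation status anyone can work out a rate difference and interval. No data are hidden. But the plan should not leave that step to the reader.

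Third, a reader might infer that the team will take non-significance as proof of equality. No passage says so. Section 9.4.2 says that significant differences lead to adjustments; it does not say only then. Other Aim 3 findings may also prompt changes, and the formal criterion is representation within plus or minus 10%. Low subgroup power is inherent in a pilot of 160 and is not itself an error.

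Finally, the race example uses chosen counts, and 3 of 8 is the outcome with the largest p-value; the table above therefore shows the other outcomes too. One might go further and suspect that differences between sites distort the racial comparison, but the documents give no basis for sizing that, and it forms no part of this point.

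**Conclusion.** The mismatch is plain on the face of the two documents and rests on no assumption: one promised comparison has no analysis in the SAP, one is not isolated, and one that the protocol rules out is tested. The missing rate difference, interval and significance level matter because 9.4.2 acts on significance while the précis and section 2.2 look for equal engagement.

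On the planned mix, a true 10-point Black v. White gap would be non-significant about three times in four (77%) and a 15-point gap about half the time (53%). A non-significant result would therefore not by itself show equal engagement. These figures assume alpha 0.05, 35% documented overall and no losses. Patients who decline are removed under section 6.2.2, which would lower power if the final numbers fall below 160. The financial-insecurity figures rest on an assumed split.

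This should be corrected, but it does not undermine the pilot's main feasibility endpoints.

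**What to change.** In the SAP:

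- Add financial insecurity v. none as a comparison of PPC documentation.
- Specify Black v. White as its own contrast, separate from any overall test of race.
- Report each difference in documentation rate with a 95% confidence interval.
- State the significance level.
- Make ethnicity descriptive only, in line with 9.4.2.

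In protocol 9.4.2, say that the estimated gap and its interval will be considered alongside the test, and that non-significance alone is not evidence of equal engagement. Whether to set a numeric gap that prompts adjustment is for the sponsor to decide.

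The cost is a few lines of text and a little more analysis, with no new data collection. Power stays as it is; the gain is that the imprecision becomes visible and the two documents agree.

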4 SELECTION AND ENROLLMENT OF PARTICIPANTS

Sample Size and Population

Patients will be recruited from geriatric and primary care clinics in three different health systems. To ensure diversity in our study population, we have purposefully engaged health systems that have higher racial and ethnic minority patient populations from the surrounding area. One of our sites is a federally qualified healthcare center, which ensures oversampling for socioeconomic diversity.

While pilot studies typically do not warrant power calculations, a target sample size can be estimated to ensure the results support progression to a full trial. Based on Lewis et al's red zone/green zone criteria, with an anticipated proportion for the upper red zone cut-off of 40% and the lower green zone cut-off of 50% for a one-sample test and 80% power (Aim 1), we will aim to recruit 160 patients or patient-care partner dyads.

We will include dyads whenever feasible, but so as not to exclude isolated adults, many who may be from historically underrepresented groups, we will allow for individuals whose physicians determine they have the capacity to understand the intervention to also participate on their own. Given that clinicians would see these individuals in clinic on their own anyway, clinician determination of capacity to participate is a pragmatic approach. This means that we act under the assumption that patients who require a care partner will have already included them in previous visits and/or provider communications (and we anticipate that this will be documented in the EHR), whereas patients who attend clinic visits independently and have no documentation indicating the involvement of a care partner in their medical decisions, or a need for one, will be determined to have the capacity to also participate in a PPC visit. PPC is designed such that even those with MCI or early dementia can engage in meaningful discussions with their provider about their preferences.

Dementia and MCI

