To identify individuals with dementia and MCI, we will use two or more instances of use of an ICD-10 code for either diagnosis in the EHR within 24 months. Typically, we would include instances of these billing codes within a year of each other, but due to the COVID-19 pandemic, we recognize that there may be less frequent clinical visits and less robust billing. We will use the following billing codes: F01.50, F01.51, F02.80, F02.81, F03.90, G30.0, G30.1, G30.8, G30.9, G31.01, G31.09, G31.1, G31.2, F41.81, G31.84 and F03.91.

Health Equity

To ensure diversity of our study population, we have purposefully engaged health systems that have higher racial and ethnic minority patient populations than the surrounding area. Furthermore, one of our sites is at a Federally Qualified Healthcare center, which ensures oversampling for socioeconomic diversity. Purposeful oversampling such as this is a well-established method for ensuring a strong signal in research data from underrepresented groups.

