5.2 Handling of Study Interventions

Following training of facilitators and providers, the research team will begin to review the

clinic schedule to identify individuals that qualify to receive the PPC intervention, based on the inclusion criteria provided.

The **intervention** will consist of the following steps:

1. Research staff will provide the PLWDM with information about PPC in a paper format with instructions to access materials in an electronic format. The paper packet will be mailed to the patient approximately 1-4 weeks prior to their next clinic visit, Electronic materials will be available online (myhealthpriorities.org). These materials will not include information about the patient's medical history or any other protected health information. No identifiable participant information will be stored on the electronic site.
 - The research team will notify facilitators and clinicians via the EHR or secure messaging to indicate which patients have been mailed a PPC packet. The method of notification will be determined based on the provider's preference.
2. Facilitators will determine the best method to engage with patients based on clinical environment and information found in the EHR. They will use clinical judgment to determine when and how to engage care partners during this step. Options might include:
 - phone calls to patients and/or care partners 1-2 weeks prior to the next clinic appointment
 - engage in discussion about the PPC packet
 - encourage the patient and/or care partner to complete the worksheet
 - engaging in PPC discussions on the day of the appointment in tandem with the clinician visit but prior to seeing the clinician
3. Research staff will send patients electronic nudges (reminders through the patient portal) approximately one to five day(s) prior to their clinic visit to engage in PPC goal setting and bring any necessary materials to their clinic visit. These nudges will be sent as clinical reminders on behalf of the clinic staff, using the electronic patient portal, and will be automated when possible.

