5.4 Adherence Assessment

Documentation of PPC discussion in 35% of eligible participants in the EHR will be ascertained using a Natural Language Processing (NLP) model. Participating clinicians will be trained to utilize the vendor “dot phrases” (pre-defined, templated language or EHR equivalent) to prompt the beginning of their PPC documentation. These dot phrases will then be incorporated into the NLP model to identify when PPC is documented within the clinical text. The NLP model will be trained to identify the dot phrases and extract details related to words following the phrase. For example: “patient care priorities were discussed, and patient wishes to...” A common script for identification of these dot phrases will be developed by the primary site and shared with the secondary site for local implementation. For the site that utilizes a different EHR vendor, a similar model will be employed ensuring the clinicians are trained to utilize similar language or programmatically input the equivalent of dot phrases. This will ensure the NLP model identifies the documentation.

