validated across the care spectrum and will be deployed at the primary site in current form on the established natural language processing platform at Regenstrief Institute. All available clinical notes for the recruited cohort will be annotated by the software as either positive or negative for the social factors. This can then be incorporated into analyses.

Given the smaller recruitment size for the secondary site, keywords from the algorithms will be shared with the study team for manual chart extraction. This process will also be utilized as controls for the programmatic implementation at the primary site.

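### Aim 3's subgroup comparisons of PPC documentation have no stated site stratification, so a gap, above all for financial insecurity, could be partly or wholly a gap between sites

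*Protocol*

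**What the plan says.** Protocol Section 9.4.2 (Aim 3) plans "between-group comparisons on our measure of PPC documentation between Black v. White and those with financial insecurity vs. none". It then attaches an action to the result: "If there are significant differences, we will make further adjustments prior to embarking upon a Stage IV ePCT of this intervention". It names no test, and Section 9.5 refers back to 9.4 for the feasibility analyses.

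The SAP compares race, ethnicity and sex between patients with and without a documented conversation, by Fisher's exact test where appropriate, two-sided. It mentions neither site nor financial insecurity.

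Four other places bear on how site enters the comparison:

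- **Socioeconomic mix (Section 4):** "One of our sites is a federally qualified healthcare center, which ensures oversampling for socioeconomic diversity".
- **Racial mix (Sections 4 and 9.1):** the health systems are described together as serving larger minority populations than the area around them. The target is given only overall: "A total of 160 patients or patient-care partner dyads (~50% White, 45% Black, and of those 6% Hispanic/Latino".
- **Outcome tool (Section 5.4):** "For the site that utilizes a different EHR vendor, a similar model will be employed", with clinicians trained to use similar language or an equivalent of the dot phrase.
- **Exposure (Section 9.1):** NLP algorithms flag social factors at the primary site. For the secondary site, "keywords from the algorithms will be shared with the study team for manual chart extraction". The manual process also serves as a control on the NLP at the primary site.

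**The concern.** Site can confound a subgroup comparison when two things hold: the subgroup mix differs by site, and the documentation rate differs by site. For financial insecurity the plan itself makes the first likely, by placing socioeconomic oversampling at one health center. The second is possible, because the documentation tool differs at one site, and Section 5.1 lets clinic leadership choose who delivers PPC. The financial-insecurity flag is also obtained in different ways at different sites, so part of any contrast may reflect how the flag was set.

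What is at stake is the action rule. A crude gap cannot show whether PPC needs tailoring for a group of patients or whether one clinic delivers or records it less. Those findings call for different changes before the Stage IV trial. Site differences in the opposite direction could also hide a real subgroup gap.

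**Working it through.** **The plan's own figure.** No sample size or power is stated for Aim 3. The 160 belongs to Aim 1 and reproduces if one-sided 5% and a continuity correction are assumed:

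- n = [(1.645 × √(0.40 × 0.60) + 0.842 × √(0.50 × 0.50)) / 0.10]² = 150.5, or 151 rounded up.
- Corrected: (150.5 / 4) × (1 + √(1 + 2 / (150.5 × 0.10)))² = 160.3.

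The point made here does not affect that figure.

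**Size of a pure site gap.** From the documents: total 160. Assumed, because the documents give no site-level values: 60 patients at the health center; financial insecurity 75% there and 15% elsewhere; documentation 20% there and 40% elsewhere, the same for both groups within a site.

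| | Insecure | Not insecure |
|---|---|---|
| Health center (60) | 45 | 15 |
| Other sites (100) | 15 | 85 |
| Expected documented | 45 × 0.20 + 15 × 0.40 = 15 | 15 × 0.20 + 85 × 0.40 = 37 |
| Crude rate | 15/60 = 25% | 37/100 = 37% |

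The crude gap is 12 points, with a within-site difference of zero. In general:

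crude gap = (difference in documentation between sites) × (share of insecure patients at the health center − share of the others there)

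Here that is 20 × (0.75 − 0.15) = 12 points. Varying the health-center size:

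| Health-center patients | Difference in shares | Gap if sites differ by 20 points | Gap if sites differ by 10 points |
|---|---|---|---|
| 40 | 30/48 − 10/112 = 0.536 | 10.7 | 5.4 |
| 60 | 45/60 − 15/100 = 0.600 | 12.0 | 6.0 |
| 80 | 60/72 − 20/88 = 0.606 | 12.1 | 6.1 |

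**Hiding a real gap.** Keep the 60-patient layout, but let the health center document more: non-insecure patients 55% there and 35% elsewhere, insecure patients 12 points lower at each. Crude rates are (45 × 0.43 + 15 × 0.23)/60 = 38% and (15 × 0.55 + 85 × 0.35)/100 = 38%. The real 12-point gap disappears.

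**How often the rule would fire falsely.** These are simulations with no within-site difference and a two-sided 5% level (assumed; the SAP states two-sided but no level). In the two-group layouts above, a crude Fisher test rejects in about 8% to 11% of trials for a 10-point site difference and 21% to 35% for 20 points. With three sites (4,000 runs each, all site inputs assumed):

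| Contrast | Subgroup share by site (%) | Documentation by site (%) | Spurious gap (points) | Crude Fisher rejects |
|---|---|---|---|---|
| Financial insecurity (90/35/35 patients) | 20/30/50 | 40/35/20 | −4.8 | 6.4% |
| | 15/25/70 | 45/35/10 | −14.1 | 38% |
| | 10/20/85 | 50/30/10 | −22.5 | 79% |
| Race, Black share (84/34/34 patients) | 40/55/58 | 45/35/25 | −2.6 | 4.7% |
| | 32/62/70 | 50/25/15 | −10.5 | 23% |
| | 25/70/80 | 55/15/10 | −21.3 | 80% |

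The race rows use about 72 Black (45% of 160) and 80 White (50%) patients. When either the mix or the documentation rate is equal across sites, the crude test rejects in 2% to 5% of runs. A site-stratified Cochran-Mantel-Haenszel (CMH) test rejects in 4% to 6% throughout.

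**Price of stratifying (60-patient example).** Mantel-Haenszel weights are 15 × 85/100 = 12.75 and 45 × 15/60 = 11.25. Within-site variances are 0.24 × (1/15 + 1/85) = 0.01882 and 0.16 × (1/45 + 1/15) = 0.01422. The standard error is √(12.75² × 0.01882 + 11.25² × 0.01422)/24 = 9.2 points. The crude value is √(0.25 × 0.75/60 + 0.37 × 0.63/100) = 7.4 points. The interval is about a quarter wider (9.2/7.4 = 1.24).

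**The case against.** The strongest objection is that a stratified analysis may answer the wrong question. Section 2.2 wants evidence that racial, ethnic and socioeconomic groups are equally engaged. If poorer patients receive less PPC because their clinic delivers less, that is a real engagement gap, and stratification would remove it from view. This stands. It rules out replacing the crude result with the stratified one, but it does not argue against showing both.

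The plan also has safeguards. Section 6.2.4 has research staff confirm documentation in the EHR, and Section 9.1 combines record review with NLP, so capture does not rest on dot phrases alone. Section 5.4 intends equivalent tools, and Section 9.1 checks NLP against manual extraction at the primary site. Table 1 lists adherence checks and interviews that may explain a gap. Differential capture is therefore possible, not established. None of these safeguards, however, removes a true difference between sites in delivery.

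Two stronger readings are tempting:

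- A reader might infer that Black and White patients are concentrated in different sites by design. The documents give no racial split by site. Section 9.4.2 sets subgroup targets against each system's own population, so the mix may differ, but nothing says that it does.
- A reader might blame unequal portal access, since "Research staff will send patients electronic nudges (reminders through the patient portal) approximately one to five day(s) prior to their clinic visit". Nothing links portal access to race, finances or site. The nudge is also one of several contacts, alongside the mailed packet, possible facilitator calls and the check-in packet. The documents give no basis for changing the nudge on this account.

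**Conclusion.** The point holds in a limited form. Section 9.4.2 makes a significant subgroup gap actionable, and the documents state no site stratification. For financial insecurity, three features tie the contrast to site: where oversampling occurs, the documentation tool, and the method of ascertainment. A crude gap there could be wholly or partly a site gap. For race the same is plausible but undocumented.

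The size cannot be computed from the documents. They give no documentation rate or subgroup mix by site, and the text available does not say whether the health center is also the site with the other EHR vendor or with manual extraction. Direction is therefore unknown too. Under the assumed inputs the artefact runs from negligible to more than 20 points; the larger values need both a strong imbalance in mix and a large site difference in documentation. This is a cheap improvement to a secondary comparison in a feasibility pilot. It does not undermine Aim 1 or the sample size.

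**What to change.** In Section 9.4.2 and the SAP, for both contrasts:

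1. Keep the crude comparison, and add the financial-insecurity contrast to the SAP, which does not mention it.
2. Add a table of documentation rates by subgroup and site, with numerators and denominators.
3. Add a site-stratified estimate, for example a Mantel-Haenszel risk difference with confidence interval, and a CMH test.
4. Base the action rule on both results. A gap that persists within site points to tailoring for the subgroup. A gap that disappears on stratification points to delivery or documentation at the site. Judge this on the two estimates and their intervals, since a stratified result can lose significance merely because its interval is wider.
5. State that the two explanations cannot be separated if a subgroup lies almost wholly in one site.
6. Report agreement between NLP and manual ascertainment of financial insecurity at the primary site, because stratification only partly deals with differing ascertainment.

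The cost is wording and two small tables. Site is already known, and the manual check at the primary site is already planned. The downside is wider intervals where a subgroup is rare at a site, about a quarter wider in the example above.
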